STATISTICAL METHODS (continued)

For the primary efficacy analysis, the treatment of missing data will be addressed using pattern mixture model methodology. Within each treatment, 4 data patterns will be defined as follows:

- Pattern 1: will include patients who completed treatment on study drug.
- Pattern 2: will include patients who discontinue treatment early due to adverse events. Missing data for these patients will be assumed to be similar to their pain score prior to the start of treatment.
- Pattern 3: will include patients who discontinue treatment early due to lack of efficacy. Missing data for these patients will be assumed to be similar to their pain score prior to the start of treatment.
- Pattern 4: will include patients who discontinue treatment early due to reasons other than adverse event or lack of efficacy. Missing data for these patients will be assumed to be similar to the scores for patients that are still in the study and randomized to the same treatment group.

The pattern mixture model methodology will be implemented using SAS procedures MI and MIANALYZE.

Sensitivity analyses will be conducted to assess the impact of the treatment of missing data on the study results. The analysis of the secondary efficacy variables is presented in Section 11 of the protocol.

Safety and Tolerability:

All safety data (AEs, clinical laboratory tests, and vital signs) will be listed by patient and summarized by group and time point as appropriate. Adverse events will be coded to preferred term (PT) and system organ class (SOC) using the Medical Dictionary for Regulatory Activities (MedDRA).

Interim Assessment

An IA is planned when approximately 50% of the planned 405 patients have been randomized and have either completed the 8-week treatment period or have discontinued from treatment early. The IA will include a re-estimation of the final target sample size based on conditional power.

SAMPLE SIZE DETERMINATION

With 270 patients assigned to active treatment and 135 patients assigned to placebo (2:1 randomization), a total sample size of 405 patients will be sufficient to detect an effect size of 0.343 with > 90% power and a type 1 error rate of 5%.

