6. SAMPLE SIZE DETERMINATION

Approximately 405 patients with OA of the hip and knee will be randomized in a 2:1 ratio (270 to CR845 and 135 to placebo) at approximately 40 sites in the United States.

A sample size re-estimation will be made after approximately 50% of the planned 405 patients have been randomized and have either completed the 8-week treatment period or have discontinued from treatment early (see Section 8.3).

The sample size will be calculated to ensure 90% conditional power such that:

$$t_2 \geq \frac{1.96 + \sqrt{0.5} t_1}{\sqrt{0.5}}$$

where t_1 and t_2 are the t-statistics from separately performing the primary analysis for stage 1 (interim) and stage 2 (post interim) patients respectively (see Section 8). Maintaining a 2:1 ratio, the required total sample size (n_2) to achieve the above criteria will be calculated using the difference between least square means and the corresponding standard error divided by $\sqrt{1/n_{11} + 1/n_{12}}$ from stage 1 analysis (where n_{11} and n_{12} are the sample size in each treatment group from stage 1).

A maximum total sample size of 480 randomized patients will be allowed for the study regardless of the sample size re-estimation at the interim analysis.

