10.1. PRIMARY EFFICACY VARIABLE

To account for the interim unblinded sample size re-assessment, the analyses relating to the primary efficacy variable will employ weighted test statistics as proposed by Cui, Hung and Wang in order to maintain the 5% two-sided type 1 error rate. As there is no potential for early stopping of the study, no adjustments need to be made to the significance levels for the combined final analysis. The primary analysis and sensitivity analyses described in this section will be performed on each stage (pre and post interim patients) separately and test statistics (t_1 and t_2) from each stage will be combined to obtain the CHW Z statistic as follows:

$Z_{CHW} = \sqrt{0.5} t_1 + \sqrt{0.5} t_2$ from which the two-sided p-value will be obtained using the normal distribution.

Point estimates and 95% CI will be obtained using methodology suggested by Hung and Lawrence²:

Point estimate:

$$\hat{\delta} = \frac{t_1 \hat{\delta}^{(1)} + \sqrt{1-t_1} \sqrt{t^* - t_1} \hat{\delta}^{(2)}}{t_1 + \sqrt{1-t_1} \sqrt{t^* - t_1}}$$

where

$t_1 = 0.5$

$t^* = (\text{Re-estimated total sample size})/405$

$\hat{\delta}^{(1)}$ = Least square mean difference from stage 1 analysis

$\hat{\delta}^{(2)}$ = Least square mean difference from stage 2 analysis

$$95\% \text{ CI} = \hat{\delta} \pm \left(\frac{\hat{\delta}}{Z_{CHW}} * 1.96 \right)$$

The primary analysis and each sensitivity analysis will also be performed using the full combined dataset with no CHW adjustment. Presentation of results will start with these analyses (additionally including the CHW results) and then follow with the results of the analysis from each individual stage.

The primary efficacy variable will be analyzed using a mixed effect model with repeated measures (MMRM). The model will contain treatment (placebo vs CR845), treatment-by-week interaction as fixed effects, baseline value and OA joint (hip vs knee) as covariates, and patient as a random effect.

The treatment difference between CR845 (across all doses) and placebo at Week 8 (the primary efficacy endpoint) will be estimated as the simple contrast in the treatment effect. The 2-sided 95% confidence interval (CI), based on the difference in the least squares (LS) means between the 2 treatment groups (CR845 vs placebo) will be presented. The LS means (and 95% CI) will be additionally be presented for each treatment for each week.

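### The SAP's CHW 95% confidence interval takes estimate/Z_CHW as its standard error, so its width can be badly wrong when the two stages disagree and the combined effect is near zero

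*SAP*

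**What the plan says.** SAP Section 10.1 adjusts for the unblinded sample size re-estimation "in order to maintain the 5% two-sided type 1 error rate". The primary and sensitivity analyses "will be performed on each stage (pre and post interim patients) separately and test statistics" from the two stages are combined as "Z_{CHW} = \sqrt{0.5} t_1 + \sqrt{0.5} t_2".

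The point estimate does not use the stage standard errors. Write d1 and d2 for the stage LS mean differences and t* for the re-estimated total divided by 405. The estimate is then (0.5·d1 + b·d2)/(0.5 + b), with b = sqrt(0.5)·sqrt(t* - 0.5). The interval is "\delta} \pm \left(\frac{\hat{\delta}}{Z_{CHW}} * 1.96", that is, estimate ± 1.96 × estimate/Z_CHW.

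On timing, SAP Section 6 states: "A sample size re-estimation will be made after approximately 50% of the planned 405 patients have been randomized". It caps the total at 480. SAP Section 10.1 adds: "The primary analysis and each sensitivity analysis will also be performed using the full combined dataset with no CHW adjustment". Those unadjusted results come first, with the CHW results beside them, followed by each stage.

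The text available gives no standard error built from the stage standard errors. It has no fallback for Z_CHW near zero, and no rule for an estimate and Z_CHW of opposite sign. SAP Section 8.3, to which Section 6 refers, is not in that text.

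**The concern.** Dividing an estimate by its test statistic recovers the standard error only when the statistic is that estimate divided by its own standard error. Here the estimate and Z_CHW are different linear combinations of d1 and d2. They agree only at one ratio of the stage standard errors, and two separate MMRM/multiple-imputation fits around an interim at roughly 50% will not give that ratio exactly.

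This is the only interval in the SAP that accounts for the sample size change, and the same rule serves the primary and the sensitivity analyses. SAP Section 8.5 makes the primary result the main guide to Phase 3 planning. After a null or weak result, the interval's width is what tells the reader which effects are still plausible, and this is where the formula fails. An interval that is far too narrow is the worse case, because it looks like precision.

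**Working it through.** **Inputs.** Two-sided 5%, critical value 1.96 (SAP 10.1); 270:135 allocation, N = 405, effect size 0.343 (Protocol Synopsis); stage weights sqrt(0.5), fraction fixed at 0.5, t* = N/405 (SAP 10.1); cap of 480 (SAP 6). The documents give no stage SDs or standard errors, so these are assumed and varied.

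**Design figure.** The Protocol Synopsis says "a total sample size of 405 patients will be sufficient to detect an effect size of 0.343 with > 90% power". In SD units SE = sqrt(1/270 + 1/135) = 0.1054; 0.343/0.1054 = 3.254; Φ(3.254 - 1.96) = 0.902. This agrees. The plan states no interval width to reproduce.

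**Algebra.** The implied standard error is

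estimate/Z_CHW = [(0.5·d1 + b·d2)/(0.5 + b)] / [sqrt(0.5)·(d1/SE1 + d2/SE2)].

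This is free of d1 and d2 only if SE2/SE1 = 0.5/b = sqrt(0.5/(t* - 0.5)), which is 1.000 at N = 405 and 0.854 at N = 480. At that ratio it is exact (0.1054 and 0.0971). It is also exact whenever d1 = d2.

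**Off that ratio.** Take N = 405, SE1 = sqrt(1/135 + 1/67.5) = 0.149, SE2 = 1.10·SE1 and d1 = 0.30. Inverting the CHW test gives a half-width of 1.96·sqrt(2)/(1/SE1 + 1/SE2) = 0.216 for every d2. The SAP formula gives:

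| d2 | SAP half-width |
|---|---|
| +0.30 | 0.216 |
| 0 | 0.207 |
| -0.20 | 0.175 |
| -0.27 | 0.114 |
| -0.29 | 0.057 |
| -0.30 | 0 |
| -0.31 | -0.114 (limits reversed) |
| -0.32 | -0.455 (limits reversed) |
| -0.33 | undefined (Z_CHW = 0) |
| -0.35 | 0.568 |

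**An extreme illustration** (assumed results, t* = 1). Let d1 = -0.30 (SE 0.34) and d2 = +0.27 (SE 0.30).
- Z_CHW = sqrt(0.5)·(-0.8824 + 0.9000) = +0.0125, and the estimate is (-0.30 + 0.27)/2 = -0.015.
- The half-width term is 1.96 × (-0.015/0.0125) = -2.36 (with Z_CHW unrounded), so the limits print in reverse order.
- A = sqrt(0.5)·(1/0.34 + 1/0.30) = 4.437, so the proper half-width is 1.96/4.437 = 0.44. Inversion gives 0.003 ± 0.44.

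**How often.** Two-sample approximation in SD units, 2:1 allocation, estimated stage standard errors, 600,000 trials per setting, no true effect, t* = 1:

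| Setting | Half-width off by more than 25% |
|---|---|
| Exact 50% split, equal SDs | 7.1% |
| Stages of 180/225 | 14.0% |
| Stages of 230/175 | 16.7% |
| Exact split, stage SDs 15% apart | 17.1% |

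In the first row, noise in the estimated standard errors is the only cause. Across the settings the interval is more than 3 times too wide in 0.7-1.7% of trials and under half the proper width in 1.2-3.0%; the ratio is negative in 0.9-2.3%. At least 99.9% of the errors above 25% had stage estimates of opposite sign. Given opposite signs, 14-34% of trials are off by more than 25%.

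**Coverage.**

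| True effect (SD) | SAP interval | CHW inversion |
|---|---|---|
| 0 | 94.9% | 94.9% |
| 0.1 | 92.8-94.1% | 94.8-94.9% |
| 0.2 | 93.5-94.5% | 94.8-94.9% |
| 0.343 | 94.6-94.9% | 94.8-94.9% |

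**With the re-estimation rule.** Stage 2 was sized for 90% conditional power, with the total held between 405 and 480 (no decrease below 405 is an assumption). The rates above 25% are 6.6%, 12.6%, 14.5% and 17% in the same order, and coverage at 0.1 is again 92.8-94.1%.

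**Combined imbalance.** If an uneven split and an SD difference act in the same direction, the rate at no effect rises to 29-31% and coverage at 0.1 falls to 91.3%. If they oppose each other, the rate stays at 7-8%.

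**The case against.** The strongest reply is that the failures fall where the result is plainly null. Among no-effect trials with width off by more than 25%, the median |Z_CHW| is 0.07-0.15 and the 99th percentile 0.57-0.92. At most 0.002% of trials were both that far off and significant. The interval equals estimate × (1 ± 1.96/Z_CHW), so it excludes zero exactly when |Z_CHW| > 1.96. The p-value, type I error and coverage at zero are therefore untouched. At 0.343, width errors above 25% occur in about 0.05-0.4% of trials at N = 405 with stage standard errors up to 20% apart. The unadjusted and stage-wise results are shown alongside, so an absurd interval would be noticed. The higher rates rest on assumed imbalances. The formulas are attributed to a published method, which was not consulted.

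All of this limits the weight of the point, and the illustration is indeed far from typical. None of it repairs the formula. A neighbouring correct result does not make a pre-specified interval right, and a half-width a quarter or a half too small does not look absurd. The 7% figure needs no imbalance at all. The point concerns the formula as the SAP applies it, with separately estimated stage standard errors, and does not dispute the cited paper.

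**Conclusion.** The concern holds. As written, the CHW interval is exact for all data only at one ratio of the stage standard errors, and it can give collapsed, exploded or reversed limits when the stages disagree around a combined effect near zero. With no effect, its half-width is off by more than 25% in about 7% of trials under the plan's own split with equal SDs, and in 14-17% under the single imbalances assumed here. Coverage at weak effects falls one to two points below nominal.

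The consequence is confined to the reported width and order of the limits in null or weak results. The CHW test is sound, and so in practice is the interval at the planned effect. The sizes rest on a two-sample approximation to the MMRM and on assumed splits and stage SDs. The algebra rests on neither. This should be corrected, but it does not threaten the primary test.

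**What to change.** Replace the two formulas in SAP Section 10.1 by inversion of the CHW test. With A = sqrt(0.5)/SE1 + sqrt(0.5)/SE2, report the estimate as Z_CHW/A and the 95% interval as Z_CHW/A ± 1.96/A. Z_CHW and its p-value do not change, and the interval is always defined, correctly ordered and consistent with the test. SE1 and SE2 already come from the stage analyses, so no new data or model programming is needed.

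The trade-off is that the estimate is then weighted by observed stage standard errors and no longer by the pre-specified fractions. The change therefore belongs in a SAP amendment before unblinding.

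A lighter alternative keeps the SAP estimate and takes its standard error directly as sqrt(0.25·SE1² + b²·SE2²)/(0.5 + b). In the 10% mismatch example this gives a half-width of 0.217, against 0.216 by inversion, but the interval will not always agree with the CHW test.

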The MMRM model will be implemented using SAS PROC MIXED. A restricted maximum likelihood (REML) will be used. The Kenward-Roger³ approximation will be used to estimate the denominator degrees of freedom and adjust standard errors. An appropriate covariance matrix will be used to model the within patient errors until there are no convergence issues in the following order: 1) unstructured, 2) Toeplitz, 3) autoregressive [1], 4) compound symmetry, 5) variance components. For analyses of multiple imputed datasets, this selection will continue until analyses for all imputations converge.

The treatment of missing data will be addressed using pattern mixture model methodology. Within each treatment, 4 data patterns will be defined as follows:

- Pattern 1: will include patients who completed treatment on study drug
- Pattern 2: will include patients who discontinue treatment early due to AEs
- Pattern 3: will include patients who discontinue treatment early due to lack of therapeutic efficacy (LOTE)
- Pattern 4: will include patients who discontinue treatment early due to reasons other than AE event or LOTE.

The pattern mixture model methodology will be implemented using SAS procedures MI and MIANALYZE. Specifically, the following steps will be followed:

- Intermittent missing data will first be imputed using the Markov Chain Monte Carlo (MCMC) method implemented with the SAS MI procedure, which is appropriate for non-monotonic missing data.
- Data for patients who discontinues early will be multiply imputed as follows:
 - If the patient discontinues due to AE (pattern 2) or LOTE (pattern 3), then missing data will be assumed to follow a distribution similar to the baseline values observed in the patient's randomized treatment.
 - If the patient discontinues due to reasons other than AE or LOTE (pattern 4), at each time point, missing data will be assumed to follow a distribution similar to scores for patients that are still in the study and randomized to the same treatment group.
- Results of the MMRM on the multiply imputed data will be summarized using the SAS MIANALYZE procedure using Rubin's rule.

A detailed plan of the above procedure is included as an attachment in Section 16.1.

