16. ATTACHMENTS

16.1. PRIMARY ANALYSIS PROGRAMMING PLAN

The primary efficacy endpoint is defined as the change from baseline at Week 8 with respect to the weekly mean of the daily 24-hour pain intensity in at the index joint.

Step 1 – Change data structure from ADaM dataset

Manipulate data into dataset (DATAIN) with multivariate structure with one record per subject and separate variables for treatment (TRTP), OA joint (STRATA) and each weekly NRS mean daily score (NRSWEEK1 to NRSWEEK8) including baseline week (BASE). Keep the reason for treatment discontinuation variable (DCTREAS). Set any imputed data (where DTYPE not missing) to missing.

Step 2 – Impute intermittent missing data

Impute intermittent missing data using the Markov Chain Monte Carlo (MCMC) method implemented with the SAS MI procedure with treatment, baseline value and OA joint (hip vs knee) included as follows (need to create numeric 0/1 variables TRTPN and STRATAN based on TRTP [CR845=1, Placebo=0] and STRATA [HIP=1, KNEE=0]):

```
proc mi data=DATAIN nimpute=100 seed=543571857 out=MONOTONIC;
var TRTPN STRATAN BASE NRSWEEK1-NRSWEEK8;
mcmc chain=multiple impute=monotone;
run;
```

This will create 100 records per subject with only monotonic missing data in the dataset MONOTONIC.

Set any imputed values <0 or >10 to 0 and 10 respectively.

Step 3 – Impute missing data due to AE or Lack of Therapeutic Effect (LOTE)

If the patient discontinues treatment due to AE or LOTE then missing data will be assumed to follow a distribution similar to the baseline values observed in the patient's randomized treatment.

- To impute missing data, the following will be performed:
 - Obtain the mean (1dp) and standard deviation (2dp) across all the patients in the treatment group at baseline (use DATAIN dataset to do this).

- Split the MONOTONIC data into 3 datasets
 - 1) Non-missing or missing and discontinued treatment not due to AE/LOTE (Both groups) – discard data
 - 2) Missing and discontinued treatment due to AE/LOTE (Placebo)
 - 3) Missing and discontinued treatment due to AE/LOTE (CR845)
- Sort the missing datasets (2 and 3) by imputation and then subject number
- Within each of the missing datasets (2 and 3), create a variable using the RANNOR function in SAS, seed=543571857, with mean and standard deviation as found above
- Impute any missing values of NRSWEEKx with the value of the created variable.
- Set any imputed values <0 or >10 to 0 and 10 respectively.

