The primary efficacy variable will be analyzed using a mixed effect model with repeated measures (MMRM). The model will contain treatment (placebo vs CR845), treatment-by-week interaction as fixed effects, baseline value and OA joint (hip vs knee) as covariates, and patient as a random effect.

```
proc mixed data=MMRMDATA;
by _Imputation_;
class TRTP AVISITN STRATA SUBJID;
model CHG = TRTP|AVISITN STRATA BASE /ddf=kr;
repeated AVISITN/SUBJECT=SUBJID type=un;
lsmeans TRTP*AVISITN/diff;
ods output Diffs=DIFF_MI LSMeans=LSM_MI;
run;
```

Check log to ensure that there are no convergence problems across all 100 analyses. If so then use different covariance structures in the following order until this is achieved:

type=toep

```
type=ar(1)  
type=cs  
type=vc
```

Extract 2 separate datasets from DIFF_MI and LSM_MI selecting the LS means (and standard errors) and difference between LS means (and standard errors) at Week 8 only. (DIFF_MI8 and LSM_MI8).

Step 7 – Combine MMRM results using Proc MIANALYZE

Use PROC MIANALYZE to obtain estimates of LS means and differences and 95% CIs.

```
proc mianalyze data=DIFF_MI8;  
model effects estimate;  
stderr sdterr;  
ods output ParameterEstimates=DIFF_MIAN8;  
run;  
  
proc mianalyze data=LSM_MI8;  
model effects estimate;  
by TRTP;  
ods output ParameterEstimates=LSM_MIAN8;  
run;
```

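### If the unstructured fit fails, every fallback covariance structure assumes one variance for all weeks, so the Week 8 standard error could be too small or too large; listing heterogeneous forms first is cheap insurance.

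*SAP*

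**What the plan says.** SAP 10.1 fits a mixed model for repeated measures to eight weekly mean pain scores and takes the Week 8 contrast as primary. The covariance structure is chosen in the order "1) unstructured, 2) Toeplitz, 3) autoregressive [1], 4) compound symmetry, 5) variance components", and for multiply imputed data "this selection will continue until analyses for all imputations converge".

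SAP 16.1 makes this operational. Step 2 creates 100 imputations ("proc mi data=DATAIN nimpute=100 seed=543571857 out=MONOTONIC"). Step 6 fits "repeated AVISITN/SUBJECT=SUBJID type=un" and then instructs: "Check log to ensure that there are no convergence problems across all 100 analyses". If there are problems, the programmer is to "use different covariance structures in the following order until this is achieved", and the listed types are toep, ar(1), cs and vc.

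Standard errors are model-based: the Kenward-Roger "approximation will be used to estimate the denominator degrees of freedom and adjust standard errors". No heterogeneous-variance structure and no robust standard error is named.

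The text of 10.1 also lists "baseline value and OA joint (hip vs knee) as covariates, and patient as a random effect", but the Step 6 code has only a REPEATED statement and no RANDOM statement.

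SAP 10.1 applies the model to each stage separately and to the combined data, for the primary and sensitivity analyses. SAP 10.2 uses the same order for the observed-data WOMAC models. Protocol 11.7.1 says only that unstructured and simpler structures (Toeplitz, AR(1), compound symmetry) will be examined. Variance components is not among its examples.

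**The concern.** The unstructured matrix gives Week 8 its own variance. The four structures after it do not: each estimates one variance and applies it to every week. The Week 8 contrast is then judged against an average over eight weeks. If Week 8 is more variable than that average, the interval is too narrow; if less variable, too wide.

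Unequal variances are plausible here. Everyone starts at one dose level and then diverges through four weeks of individual titration. The baseline week adjoins Week 1, so it may predict later weeks less well. Patients who stop for adverse events or lack of efficacy receive random draws from their arm's baseline distribution, and the share of such values can only grow by week.

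The Week 8 standard error produces the two stage statistics that the CHW test combines to hold the 5% level (SAP 10.1). The stage 1 standard error also enters the sample size re-estimation (SAP 6).

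As coded, variance components also sets the within-patient correlation to zero, which could affect analyses that use several weeks or have missing weeks.

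**Working it through.** **The plan's own figure.** The Synopsis states more than 90% power for 270:135 and an effect size of 0.343. The standard error of the standardised difference is √(1/270 + 1/135) = 0.1054; 0.343/0.1054 = 3.254; power = Φ(3.254 − 1.96) = 0.902 (0.901 with the t distribution). It reproduces, and it takes the Week 8 standard error as correctly estimated.

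**Inputs from the documents.** Eight weeks, so 8 × 9/2 = 36 unstructured parameters; 100 imputations; two-sided 5%; about 405 × 0.5 ≈ 202 patients in stage 1; the order above.

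**Assumed.** The documents give no weekly SDs or correlations. Take the SD as linear from 1 at Week 1 to r at Week 8.

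**Step 1, standard error under a common variance.** Mean of the squared SDs = 1 + (r − 1) + 0.357(r − 1)², where 0.357 = (0² + 1² + … + 7²)/(49 × 8) = 140/392. The standard error ratio (reported/correct) is √(mean square)/r, and the actual two-sided error is 2[1 − Φ(1.96 × ratio)].

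| r | mean square | SE ratio | error |
|---|---|---|---|
| 0.8 | 0.814 | 1.128 | 0.027 |
| 1.0 | 1.000 | 1.000 | 0.050 |
| 1.15 | 1.158 | 0.936 | 0.067 |
| 1.3 | 1.332 | 0.888 | 0.082 |
| 1.5 | 1.589 | 0.840 | 0.100 |
| 1.7 | 1.875 | 0.805 | 0.114 |

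The formula is exact for compound symmetry and variance components in large complete samples. The large-sample fits of Toeplitz and AR(1), under three correlation shapes, agree with it within about 0.01. Simulation with 20,000 runs gave 0.084 (405 patients) and 0.083 (202 patients) at r = 1.3, and 0.100 and 0.099 at r = 1.5. A Week 8-specific variance gave 0.048 to 0.053 throughout.

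**Step 2, adding between-imputation variance.** Step 1 covers only within-imputation variance. SAP 10.1 combines by Rubin's rule, which adds between-imputation variance that the covariance structure leaves largely untouched. Simulation of a 202-patient stage (2:1, baseline draws after adverse-event or lack-of-efficacy dropout, 20 imputations, 6,000 runs, AR(1) correlation 0.85, baseline SD 1.2, all assumed) gave these errors under a common variance:

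| SD, Week 1 to 8 | Step 1 formula | 10% dropout | 20% | 30% |
|---|---|---|---|---|
| 1.3 to 2.2 | 0.114 | 0.098 | 0.082 | 0.070 |
| 1.6 to 2.2 | 0.089 | 0.078 | 0.065 | 0.055 |
| 1.8 to 2.2 | 0.074 | 0.066 | 0.054 | 0.047 |

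The unstructured model gave 0.036 to 0.044 in the same settings.

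**Step 3, does the imputation itself create unequal variance?** With equal underlying weekly SDs of 1.5 or 2.0 and 10–30% such dropout (assumed), the pooled/Week 8 standard error ratio was 0.955 to 0.997, that is, about 0% to 5% too small.

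**Step 4, independence under variance components.** For the Week 8 contrast in completed data it adds nothing to Step 1. For a WOMAC contrast averaging Weeks 4, 6 and 8 with equal variances and correlation ρ, the true variance is proportional to (1 + 2ρ)/3 and the fitted one to 1/3, so the ratio is 1/√(1 + 2ρ). For ρ = 0.5, 0.7, 0.8 (assumed) it is 0.71, 0.65, 0.62, with error 0.17, 0.21, 0.22.

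**The case against.** The trigger is remote. The primary model is fitted to completed data with about 200 patients per stage for 36 parameters. An unstructured REML fit to 300 simulated imputed datasets of 202 patients had no failures and needed at most 9 iterations. That was not PROC MIXED, so it is indicative only. The point stands and sets the priority: this is insurance.

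The order is also pre-specified and not driven by the result, and its first three fallbacks are structures the protocol names. That is good practice, but it does not make a common variance right for a single-week contrast.

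A reader might infer that one failure in 100 leads to independence and a wrong Week 8 standard error, so that the 5% level is lost. The documents do not support that. One failure leads to Toeplitz; independence needs four successive failures. If the random patient effect in the text were fitted, variance components would amount to compound symmetry. With equal variances there is no error, and with falling variance the test is conservative. Nothing in the documents shows that the variance of change rises by week. The 11% error is the steepest assumed path before between-imputation variance is added, close to a no-dropout upper bound.

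A sandwich standard error cannot be combined with Kenward-Roger in PROC MIXED, so it would displace a planned method. That is a trade-off, not a plain improvement.

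**Conclusion.** The gap is real but conditional. It needs two things: a failed unstructured fit, and a Week 8 variance that differs from the average over weeks. Given both, the Week 8 standard error is off by roughly +13% to −19% for SD ratios of 0.8 to 1.7. The two-sided error is then about 0.03 to 0.11 before between-imputation variance. With 20–30% adverse-event or lack-of-efficacy dropout, the mildest rising path simulated shows essentially no inflation. SD paths, correlations and dropout rates are all assumptions.

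Zero correlation under variance components matters little for the primary contrast in completed data. It can matter for the observed-data model, where correlation carries information about missing weeks (not computed here). It can also matter for WOMAC, if the Weeks 4, 6 and 8 comparison in SAP 10.2 means their average; the wording does not settle this.

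A low-priority improvement, worth making because it is nearly free.

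**What to change.** Before unblinding, change the order in SAP 10.1, 10.2 and 16.1 (Step 6) to un, toeph, arh(1), csh. Place homogeneous forms after these, if they are kept at all. Delete variance components. Keep Kenward-Roger; a sandwich standard error for a fallback is optional, with the loss noted above.

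For eight weeks the heterogeneous forms need 15 (8 variances + 7 correlations), 9 and 9 parameters against 36 for unstructured, so they remain real simplifications.

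In the same edit, reconcile the random patient effect in the text with the REPEATED-only code.

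The cost is a few words in three places and a few lines of code. There is no effect on data collection, sample size or the primary model if the unstructured fit converges.
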